7.0 Risks

The risks include all those that come with undergoing prostatic enucleation. That includes: urinary tract infection (<5%), urinary leakage (<5%), bleeding(<2%).

8.0 Reporting of Adverse Events or Unanticipated Problems involving Risk to Participants or Others

Any adverse events or anticipated problems will be reported to the IRB by the PI within 5 business days of the discovery.

9.0 Study Withdrawal/Discontinuation

Subjects would be withdrawn from the study if their anatomy complicates the assigned prostate surgery or intraoperatively, access is unobtainable in a retrograde fashion. Subjects may withdraw from the study at any time.

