3.0 Animal Studies and Previous Human Studies

There are no previously published articles examining animal studies related to Moses fiber enucleation of the prostate. Currently, laser enucleation of the prostate with standard holmium or thulium lasers is routinely performed for BPH. Though Moses technology operates similar to other lasers on the market and has been shown to be safe in humans, it has not been evaluated for surgical outcomes.

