4.0 Inclusion/Exclusion Criteria

- Exclusion criteria
 - 1. Pediatric patients (<18 years old)
 - 2. Abnormal anatomy precluding enucleation
- Inclusion
 - 1. Patients with planned prostatic enucleation for BPH.

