5.0 Enrollment/Randomization

We will identify patients scheduled to undergo laser enucleation of the prostate for BPH through our urology clinic. Power analysis to detect a 50% change in blood loss (i.e. a change in hemoglobin level) will lead to approximately 20 patients in each group. A random number generator will be used at the beginning of each case after the induction of anesthesia to randomize patients to MoLEP or HoLEP.

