6.0 Study Procedures

Patients will be consented in our clinic after being scheduled for surgery. All patients will fill out voiding symptom scores (i.e. International Prostate Symptom Scores(IPSS)), erectile dysfunction symptom scores (i.e. Sexual Health Inventory for Men(SHIM)) and have a preoperative urine flow, postvoid volume and a prostate specific antigen (PSA) recorded. Intraoperatively, total surgery time, as well as enucleation and morcellation times, will be recorded. Furthermore, intraoperative blood loss and surgical complications will be evaluated. Postoperatively, all patients will be observed overnight in the hospital with a urethral catheter. Routine labs will be sent including a complete blood count and metabolic panel. Postoperative day one, all patients will undergo a voiding trial for catheter removal. Patients will be monitored for routine complications after HoLEP such as urinary retention, urosepsis, urinary leakage. Other variables to be recorded will be age, sex, size of prostate, BMI, anticoagulation status, and other comorbidities. Patients will follow up at 4 weeks for a postoperative check and evaluation of symptoms (i.e. IPSS, SHIM, flow rate, postvoid residual volume and PSA).

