Vanderbilt University Medical Center
Department of Urologic Surgery
[REDACTED]
[REDACTED]

Statistical Analysis Plan
Date: 12/21/2021

NCT04263987

**Evaluation of the Moses Laser for Prostate
Enucleation**

[name]

Clinical Instructor of Urologic Surgery
Vanderbilt University Medical Center
Department of Urologic Surgery

Power and Statistical Analysis

Power analysis was performed for sample size estimation based on prior reports from the literature, which previously estimated a 20% improvement in operative time when performing M-HoLEP. A sample size of 60 subjects had greater than 80% power to detect this change with $\alpha=0.05$. Continuous and categorical variables were compared using the Student T-test (2-tailed) and Fisher exact test, respectively. Multiple linear regression was performed to evaluate for the effect of the MOSES technique on operative time controlling for age, Charlson comorbidity index, change in hematocrit, and the amount of prostatic tissue enucleated. All testing was performed with $p < 0.05$ as significant. All analyses were conducted in Stata 14.2 (StataCorp, College Station, Texas).

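### Patients may be withdrawn after randomisation for anatomy that complicates the assigned operation, and no analysis set says whether they still count; any bias is conditional and small to modest

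*Protocol*

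**What the plan says.** Protocol section 5.0 sets the time of allocation: "A random number generator will be used at the beginning of each case after the induction of anesthesia to randomize patients". Section 9.0 gives two grounds on which the study team withdraws a subject. The first is anatomy: "Subjects would be withdrawn from the study if their anatomy complicates the assigned prostate surgery". The second applies where "intraoperatively, access is unobtainable in a retrograde fashion". Patients may also leave by choice: "Subjects may withdraw from the study at any time".

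Anatomy also appears in section 4.0 as an exclusion criterion: "Abnormal anatomy precluding enucleation".

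On the data, section 6.0 says: "Intraoperatively, total surgery time, as well as enucleation and morcellation times, will be recorded". The SAP's single methods paragraph says: "Continuous and categorical variables were compared using the Student T-test (2-tailed) and Fisher exact test, respectively". It adds a linear regression of operative time on technique with four covariates, one of which is the quantity of tissue removed. Neither document names an analysis population. Neither says whether a withdrawn patient's data are kept, or how an operation stopped early enters the operative-time analysis. Neither mentions blinding.

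**The concern.** Surgery can be *assigned* only after the draw, so the anatomy ground appears to operate after randomisation, although section 9.0 gives it no explicit time. *Complicates* is undefined and is judged against the arm received. The operator very probably makes that decision and can hardly be unaware of which laser is in use; that is an inference.

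Withdrawal from the study can readily be read as removal from the analysis, and the SAP does not exclude that reading. Difficult anatomy is plausibly linked to longer operations and more bleeding. If more difficult cases leave one arm than the other, the remaining groups are no longer the randomised groups. Operative time, on which the SAP is powered, and blood loss, a stated aim in protocol section 2.0, could both shift. The regression cannot repair this, because it uses only the patients who remain.

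A related gap is the operation stopped before enucleation. It has a short elapsed time and little or no tissue weight, and entered as it stands it would look like a fast procedure.

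**Working it through.** **1. Order of events.** The draw comes at the start of the case (section 5.0). Both withdrawal grounds in section 9.0 follow it on their wording: one refers to the assigned surgery, the other to an intraoperative finding. The grounds differ in kind. Access is gained before either laser is used, so its failure is unlikely to depend on the arm. It mainly reduces numbers. Only the anatomy ground refers to the arm, so only it carries the bias argument.

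**2. The SAP's own figure.** The SAP gives 60 subjects, a 20% improvement, more than 80% power and alpha 0.05. It gives no SD and no split, so 30 per arm is assumed. With equal variances the noncentrality is (0.20 / CV) × √(30/2), where CV = SD/mean. Power is 80.5% at CV 0.27, just under 80% at 0.272 and 72% at 0.30. If times are lognormal and the faster arm's times are multiplied by 0.8, its SD shrinks too. Simulated t-test power is then 88.3% at CV 0.27, 81.0% at 0.30 and 79.7% at 0.305. So 0.30 is about the largest spread consistent with the SAP in that model, and it is used below.

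**3. Illustration for operative time.** Assumptions, none from the documents:
- lognormal times with mean 1 and no true difference;
- perceived difficulty = r × z + √(1 − r²) × e, where z is the standardised log time and e is independent noise;
- the k most difficult of 30 are dropped;
- two-sided Student t-test at 0.05, with at least 200,000 simulated trials per cell (Monte Carlo SE about 0.05 points or less).

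| Dropped (arm A + arm B) | r = 0.5: shift / type I error | r = 0.2: shift / type I error |
|---|---|---|
| 0 + 0 | 0 / 5.0% | 0 / 4.9% |
| 2 + 0 | -2.1% / 6.0% | -0.8% / 5.2% |
| 3 + 0 | -3.0% / 6.7% | -1.1% / about 5.2% |
| 2 + 1 | -1.0% / about 5.5% | -0.4% / 5.0% |
| 2 + 2 | 0 / 5.4% | 0 / 5.0% |

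**4. Hand check.** The log-scale SD is s = √ln(1 + 0.30²) = 0.294. The expected two largest of 30 standard normal values are 2.04 and 1.62, mean 1.83. At r = 0.5 the dropped cases average about exp(0.147 × 1.83 − 0.147²/2) = 1.29. The shift is −(2/28) × 0.29 = −2.1%. For three dropped, the third largest is 1.36 and the mean 1.67, so the dropped cases average about 1.26 and the shift is −(3/27) × 0.26 = −2.9%. Both agree with the simulation.

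**5. Scale.** Against the 20% target, the one-arm shifts at r = 0.5 are 2.1/20 = 10.5% and 3.0/20 = 15% of the effect sought. At CV 0.27 and r = 0.5 they are -1.9% and -2.6%, with type I error of about 6.0% and 6.7%. The documents give no basis for a blood-loss figure.

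**The case against.** The harm needs several things to hold together: anatomy withdrawals occur after the draw, the patients are then left out, withdrawals differ by arm, and difficulty tracks operative time. The wording supports only the first. Leaving the study does not in itself mean that recorded data are discarded. Section 3.0 also suggests that the arms may be affected alike: "Though Moses technology operates similar to other lasers on the market". The illustration chooses one-arm loss of the most difficult cases, and at correlation 0.2 the effect nearly vanishes. All of this stands, and it limits the conclusion to a conditional one. It does not remove the point, because a discretionary, arm-referenced rule is written into the protocol and no analysis set offsets it.

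Four stronger readings are tempting and unsupported.
- *The comparison is biased.* Differential withdrawal is not shown, and the documents give no withdrawal rate.
- *Both grounds bias the result.* Failed access precedes use of the laser, and if it is equally frequent in both arms it costs precision only.
- *Sections 4.0 and 9.0 contradict each other.* A bar to eligibility and a ground for withdrawal may have different thresholds. What is missing is a definition and a statement of how they relate.
- *The inflation is large.* Removing the 2 or 3 longest operations outright from one arm at CV 0.25 gives type I error of about 9% or 12.5%, but the rule selects on judged anatomy, not on observed time.

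**Conclusion.** The point holds in a limited form. After allocation, the protocol permits withdrawal on an undefined judgement tied to the assigned arm, and the SAP does not say whether those patients are analysed. The existence of the rule and of the gap is well supported; that they cause bias is only possible.

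If two or three difficult cases were lost from one arm only, the operative-time comparison would shift by roughly 1% to 3% and type I error would rise from 5% to between about 5.2% and 6.7%, for correlations from 0.2 to 0.5. Balanced loss for the same reasons gives no mean shift. These sizes rest on assumed spread, correlation and withdrawal counts. The actual size and direction are unknown. The correction is cheap and should be made.

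**What to change.** 1. If enrolment is still open, draw the random number after retrograde access and anatomy have been checked and before the laser is used. Most such exclusions then precede assignment.
2. State in protocol section 9.0 and in the SAP that an anatomy withdrawal does not remove a randomised patient from the analysis. Patients whose surgery is completed are analysed in the assigned arm for all outcomes, unless a patient who withdraws voluntarily does not allow use of the data.
3. For operations stopped before completion, do not treat elapsed time as a short operation. Report operative time as not completed, say plainly that these cases are outside the operative-time t-test and regression, and keep their other recorded outcomes in the assigned arm. Tabulate all post-randomisation withdrawals and stopped cases by arm and reason. The operative-time result then describes completed operations, and the table lets a reader judge whether the arms remain comparable.
4. Clarify how the anatomy wording of section 9.0 relates to that of section 4.0. No clinical rule is proposed here.

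The cost is a small change in the timing of the draw, some wording, one table and slightly more variance from atypical cases. The SAP is written in the past tense, so item 1 may no longer be possible; items 2 and 3 would still apply as far as data were kept.

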10.0 Privacy/Confidentiality Issues

Any information obtained will remain confidential and patient records will be de-identified. All information will be stored in password encrypted files. The results of the project may be made public and information published in profession journals, but no identifying information will be published.

11.0 Follow-up and Record Retention

It is anticipated the data collection will take 12 months to complete, and another 12 months to analyze the data. All identifiers will be destroyed 4 years after the study initiation, or 2 years after data collection is complete, whichever is sooner.

Vanderbilt University Medical Center
Department of Urologic Surgery
[REDACTED]
[REDACTED]

Statistical Analysis Plan
Date: 12/21/2021

NCT04263987

**Evaluation of the Moses Laser for Prostate
Enucleation**

[name]

Clinical Instructor of Urologic Surgery
Vanderbilt University Medical Center
Department of Urologic Surgery

Power and Statistical Analysis

Power analysis was performed for sample size estimation based on prior reports from the literature, which previously estimated a 20% improvement in operative time when performing M-HoLEP. A sample size of 60 subjects had greater than 80% power to detect this change with $\alpha=0.05$. Continuous and categorical variables were compared using the Student T-test (2-tailed) and Fisher exact test, respectively. Multiple linear regression was performed to evaluate for the effect of the MOSES technique on operative time controlling for age, Charlson comorbidity index, change in hematocrit, and the amount of prostatic tissue enucleated. All testing was performed with $p < 0.05$ as significant. All analyses were conducted in Stata 14.2 (StataCorp, College Station, Texas).

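### The 4-week IPSS, SHIM, flow rate, postvoid residual and PSA get only an unadjusted t-test on an unstated scale, although each has a preoperative value that could be used as a covariate

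*SAP*

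**What the plan says.** Protocol section 6.0 (Study Procedures) plans two measurements of the same five variables.

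- **Before surgery:** "All patients will fill out voiding symptom scores", together with the SHIM, and patients "have a preoperative urine flow, postvoid volume and a prostate specific antigen (PSA) recorded".
- **After surgery:** "Patients will follow up at 4 weeks for a postoperative check" and "evaluation of symptoms (i.e. IPSS, SHIM, flow rate, postvoid residual volume and PSA").

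The SAP (Power and Statistical Analysis) names none of the five. They fall under its general sentence: "Continuous and categorical variables were compared using the Student T-test (2-tailed) and Fisher exact test, respectively". The only covariate-adjusted analysis concerns a different outcome: "Multiple linear regression was performed to evaluate for the effect of the MOSES technique on operative time". Its covariates are age, a comorbidity index, hematocrit change and the quantity of tissue removed, so no preoperative value of the five measures enters any model.

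Aim 2 in protocol section 2.0 speaks of changes and of improvement in quality of life. That leans towards a change score, but it states an aim and does not define an analysis variable.

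**The concern.** Two things are left on the table. First, a preoperative value is usually one of the better available predictors of the same measure at follow-up, and a two-sample t-test on 4-week values ignores it. A t-test on change uses it only by subtraction, which in effect fixes the baseline slope at 1 whatever the data show.

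Second, the scale is not stated. Two analysts following the SAP could test different quantities for five outcomes and report different estimates, intervals and p-values from the same patients.

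The trial is small (60 subjects in the SAP, about 20 per group in protocol section 5.0), so precision is scarce. Neither sample-size calculation is touched: the SAP's rests on operative time and the protocol's on hemoglobin change. The five measures are secondary to those. What is at stake is how informative the functional comparison under Aim 2 can be.

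**Working it through.** **The plan's own figure.** The SAP bases its sample size on prior reports "which previously estimated a 20% improvement in operative time" and says "A sample size of 60 subjects had greater than 80% power to detect this change". It gives no mean or SD, so this cannot be reproduced. With 30 per arm and a two-sided 0.05 t-test, power above 80% for a 20% difference requires a coefficient of variation of at most about 0.272. The point below does not depend on this.

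**Inputs.** From the documents: N = 60 (SAP) or about 40 (protocol, 20 per group), and two-sided alpha 0.05. Assumed, because the documents do not give them:
- 1:1 allocation
- normal data, with the same SD and correlation in both arms
- complete baselines
- pre/post correlation ρ of 0, 0.2, 0.3, 0.5 and 0.7
- k = preoperative SD / 4-week SD of 0.5, 1 and 1.5

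**Formulas**, each relative to the variance of a 4-week t-test:
- Adjusted for baseline: (1 − ρ²) × (N − 3)/(N − 4). The second factor is the price of estimating the baseline slope: 57/56 = 1.018 at N = 60 and 37/36 = 1.028 at N = 40.
- Change score: 1 + k² − 2ρk.
- Confidence-interval width ratio: √(variance ratio) × t(0.975, N − 3)/t(0.975, N − 2).

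Example at ρ = 0.5, N = 60: variance 0.75 × 1.018 = 0.763; width √0.763 × (2.0025/2.0017) = 0.874.

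**Adjusted analysis against a 4-week t-test**

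| ρ | 0 | 0.2 | 0.3 | 0.5 | 0.7 |
|---|---|---|---|---|---|
| Variance, N = 60 | 1.018 | 0.977 | 0.926 | 0.763 | 0.519 |
| CI width, N = 60 | 1.009 | 0.989 | 0.963 | 0.874 | 0.721 |
| Variance, N = 40 | 1.028 | 0.987 | 0.935 | 0.771 | 0.524 |
| CI width, N = 40 | 1.015 | 0.994 | 0.968 | 0.879 | 0.725 |

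Break-even is where (1 − ρ²)(N − 3)/(N − 4) = 1, which is ρ = 0.132 at N = 60 and 0.164 at N = 40.

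**Change score against a 4-week t-test (variance)**

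| ρ | 0 | 0.2 | 0.3 | 0.5 | 0.7 |
|---|---|---|---|---|---|
| k = 0.5 | 1.25 | 1.05 | 0.95 | 0.75 | 0.55 |
| k = 1 | 2.00 | 1.60 | 1.40 | 1.00 | 0.60 |
| k = 1.5 | 3.25 | 2.65 | 2.35 | 1.75 | 1.15 |

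The unstated choice of scale can therefore cut the variance by nearly half or more than triple it.

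**Adjusted analysis against a change-score t-test (CI width, N = 60)**

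| ρ | 0 | 0.2 | 0.3 | 0.5 | 0.7 |
|---|---|---|---|---|---|
| k = 0.5 | 0.903 | 0.965 | 0.988 | 1.009 | 0.972 |
| k = 1 | 0.714 | 0.782 | 0.814 | 0.874 | 0.930 |
| k = 1.5 | 0.560 | 0.607 | 0.628 | 0.661 | 0.672 |

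**Worst case for adjustment.** (1 + k² − 2ρk) − (1 − ρ²) = (k − ρ)² ≥ 0, and 1 − ρ² ≤ 1. So the adjusted variance is at most (N − 3)/(N − 4) times that of either t-test, whatever ρ and k are: 1.8% more at N = 60 and 2.8% more at N = 40.

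**Power at 30 per arm** (noncentral t; both effects are illustrative, in 4-week SD units)

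| Effect | 4-week t-test | Adjusted, ρ = 0 / 0.2 / 0.3 / 0.5 / 0.7 |
|---|---|---|
| 0.5 SD | 48% | 47 / 49 / 51 / 59 / 75% |
| 0.736 SD | 80% | 79 / 81 / 83 / 89 / 97% |

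For the 0.736 SD effect with k = 1, a change-score t-test has 66% power at ρ = 0.3, 80% at 0.5 and 95% at 0.7.

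**The case against.** The strongest case against acting has four parts.

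1. **A t-test in a randomized trial is legitimate.** No bias, inflated error rate or wrong conclusion has been shown, so adjustment is only a preference for efficiency. The first part stands: this is a loss of precision, not a validity error. The open choice between 4-week value and change is a separate gap in pre-specification, and it remains even if ρ is low.

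2. **The gain rests on an unknown ρ.** Surgery removes the tissue that drives the preoperative values, so a strong correlation cannot be presumed. This stands as a limit on the size. Below ρ = 0.2 there is almost nothing to gain over a 4-week t-test, and below 0.13 there is a trivial loss. It does not change the choice, because the loss is capped at 2–3% of variance while the gain can approach half.

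3. **The cap assumes normal data and complete baselines.** On normality, a check with lognormal data at 30 per arm gave adjusted/4-week variance ratios of 1.01, 0.95 and 0.78 at underlying correlations 0, 0.3 and 0.5, so skewness does not overturn it. On completeness, the objection is right that a complete-case regression drops a patient without a preoperative value. With 5 of 60 missing at ρ = 0.3, the ratio is 0.91 × (52/51) × (60/55) = 1.01, so the gain disappears. Section 6.0 plans these measurements for all patients, and even this example costs about 1% of variance.

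4. **The SAP is written in the past tense**, so replacing the test may no longer be possible. That stands, and it governs how the fix is presented.

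**Conclusion.** The concern holds. All five measures have a planned preoperative value that the SAP does not use as a covariate, and the SAP does not say which quantity its t-test compares. Against a 4-week t-test at 30 per arm, the cost is from nothing (ρ below about 0.13) to intervals that could have been 28% narrower (ρ = 0.7), with 13% at ρ = 0.5. Against a change-score t-test, the adjusted interval runs from 1% wider to 44% narrower over the values examined.

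These sizes rest on 1:1 allocation, equal SDs and correlation in the two arms, complete baselines, and assumed values of ρ and k. The cap on the downside needs neither ρ nor k. The change should be made, but it concerns secondary outcomes and affects neither the powered outcome nor the validity of the trial.

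**What to change.** For each of the five measures, replace the t-test with a linear regression of the 4-week value on arm and the preoperative value of the same measure. Report the adjusted difference between arms with its 95% confidence interval. Because arm and baseline are both in the model, the choice between 4-week value and change no longer alters the treatment comparison. Name in the SAP any measure to be analysed on a log scale, say how zero values are handled, and report an adjusted ratio for it. State also how a missing preoperative value is handled, so that patients are not dropped by default.

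If the t-tests have already been run, report them, say which scale they used, and present the adjusted results as a disclosed post hoc supplement.

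The cost is a few sentences in the SAP and one regression command per measure. The SAP already uses multiple linear regression, and no new data are needed. The statistical price is one degree of freedom.

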1.0 Background

Benign prostatic hypertrophy (BPH) is common with almost 50% of men having pathologic changes in the prostate between 50 and 60 years old¹. There are many options for the treatment of BPH, though a minimally invasive approach has been favorable over the past decade. Enucleation of a prostate with a laser has become a mainstay of BPH treatment and has shown to be safe and effective. Traditionally, a holmium laser is used for this (i.e. Holmium laser enucleation of the prostate or HoLEP), though recent new technologies have been developed to improve laser surgery. One example is the Moses laser fiber produced by Lumenis (Yokneam, Israel), which alters laser pulse wave characteristics to improve the efficiency of energy delivery to a target. The technology is hypothesized to lead to better improvements in operative time and hemostasis ^{2,3,4}. Though the technology has been proven to be safe in human use, it has not been formally evaluated for prostatic enucleation. We seek to compare HoLEP to Moses laser enucleation of the prostate (i.e. MoLEP) for the treatment of BPH.

1. Berry SJ, Coffey DS, Walsh PC, Ewing LL. The development of human benign prostatic hyperplasia with age. *J urol* 1084; 132(3):474-479.
3. Mark Cynk, Holmium Laser Enucleation of the Prostate is More Efficient with More Laser Power, abstract #MP7- 01, Moderated Poster Session 7: BPH/LUTS, WCE 2016

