2.0 Rationale and Specific Aims

The aims of this study are to:

1. Evaluate Moses laser technology for prostatic enucleation compared to traditional holmium laser enucleation.
2. Determine changes in blood loss, operative times, and quality of life improvements between the two technologies.

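### The operative-time regression adjusts for change in hematocrit, a post-randomization measure of the bleeding the laser is expected to change, so its MOSES coefficient need not be the total effect

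*SAP*

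**What the plan says.** The SAP (Power and Statistical Analysis) bases its power statement on operative time. It then describes two analyses that apply to that outcome. The first is general: "Continuous and categorical variables were compared using the Student T-test (2-tailed) and Fisher exact test, respectively". The second is specific to this outcome and to the laser: "Multiple linear regression was performed to evaluate for the effect of the MOSES technique on operative time". Two of the covariates in that model are baseline characteristics and two are known only once surgery is over; the SAP lists them as "controlling for age, Charlson comorbidity index, change in hematocrit, and the amount of prostatic tissue enucleated". It does not say which of the two analyses is the main comparison. It gives no reason for adjusting for hematocrit and does not describe the coefficient as a direct effect.

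The protocol fixes the timing. Section 5.0 states: "A random number generator will be used at the beginning of each case after the induction of anesthesia". Section 6.0 sends the blood count after surgery.

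The protocol also treats bleeding as something the laser may change. Section 1.0 states: "The technology is hypothesized to lead to better improvements in operative time and hemostasis". The second aim in section 2.0 reads: "Determine changes in blood loss, operative times, and quality of life improvements between the two technologies". Section 5.0 sizes the trial on a 50% change in blood loss, expressed as a change in hemoglobin.

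**The concern.** Randomization protects a comparison of the arms as randomized, or one adjusted for variables fixed before assignment. Change in hematocrit is neither: part of it arises during and after the operation being timed. Holding it constant asks how the lasers would compare if bleeding were the same, which is not the question the SAP sets for this model.

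This does not rest on one causal account. The coefficient shifts if bleeding prolongs surgery, if longer surgery causes more bleeding, or if something unmeasured drives both. The condition is that MOSES changes hematocrit by some route, including simply by shortening the operation, and that hematocrit is associated with time within arms. If either part fails, there is no bias.

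At stake is the only analysis the SAP explicitly describes as evaluating the MOSES effect on the outcome it is powered on.

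**Working it through.** **1. The plan's own figure.** The SAP gives a 20% difference, 60 subjects, alpha 0.05 and power above 80%, but no SD, so the power cannot be reproduced. Assume 30 per arm and a two-sided t-test with 58 df and noncentrality 0.20 / (CV × √(2/30)), where CV is SD over control mean. Power is 97% at CV 0.20, 86% at 0.25, 72% at 0.30 and 48% at 0.40. Exactly 80% needs CV 0.2719, an effect of 0.20 / 0.2719 = 0.736 SD. That boundary case is used below. The concern does not depend on it.

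**2. Formula.** Let τ be the true saving in SDs of time, and δ the amount by which MOSES reduces the hematocrit fall, in SDs. Let r be the within-arm correlation of that fall with time given prostate size, and R² the share of time variance explained by size. Then

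adjusted saving = τ − δ × r × √(1 − R²).

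The documents give none of δ, r or R²; all are assumed. Power comes from 20,000 simulated trials per scenario (Monte Carlo error about 0.3 points). Age and Charlson index were simulated as unrelated to time, and tissue as correlated 0.9 with size.

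**3. Results at r = 0.3, τ = 0.736.**

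| R² | δ | Adjusted saving (SD) | Power, SAP model | Power, same model without hematocrit |
|---|---|---|---|---|
| 0.4 | 0 | 0.736 | 93% | 91% |
| 0.4 | 0.2 | 0.736 − 0.2×0.3×0.775 = 0.690 | 89% | 91% |
| 0.4 | 0.5 | 0.736 − 0.5×0.3×0.775 = 0.620 | 80% | 91% |
| 0.2 | 0 | 0.736 | 87% | about 85% |
| 0.2 | 0.2 | 0.736 − 0.2×0.3×0.894 = 0.682 | 81% | about 85% |
| 0.2 | 0.5 | 0.736 − 0.5×0.3×0.894 = 0.602 | 69% | about 85% |

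The t-test has about 80% power throughout. Simulated estimates matched the formula within 0.005 SD. The largest shift in the grid (δ up to 0.5, r up to 0.4) is at δ = 0.5, r = 0.4, R² = 0.2: 0.5×0.4×0.894 = 0.179, leaving 0.557 SD, a 24% understatement. At r = 0.1 the shift is at most 0.5×0.1×0.894 = 0.045 SD.

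**4. No direct laser effect on bleeding.** Suppose the hematocrit fall depends only on operating time, with within-arm correlation ρ. Tissue explains q = 0.9² × R² of time variance, and the adjusted saving is τ(1 − ρ²) / (1 − ρ²q). For ρ = 0.3 / 0.4 this gives 0.68 / 0.63 SD at R² = 0.2 and 0.69 / 0.65 SD at R² = 0.4. A real time saving is enough to produce the bias.

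**5. Separate check in percent of control mean.** Take a total effect of −20 and SD 27, with r now unadjusted for size and g the MOSES effect on the hematocrit fall in SDs. The adjusted effect is −20 − r × 27 × g.

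- r = 0.2, g = −0.25: −18.7 (93% of the total)
- r = 0.4, g = −0.5: −14.6 (73%)
- r = 0.6, g = −0.75: −7.9 (39%)
- r = 0.4, g = +0.5: −25.4 (overstated)

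Simulating 2,000,000 records at r = 0.4 gave −20.0 unadjusted under all three structures. Adjusted, it gave −14.6 with hematocrit as mediator, −16.8 as a consequence of time, and −14.6 with a shared unmeasured cause.

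**6. No true total effect on time.** The SAP model rejects in about 6% of trials at δ = 0.2 and in 8 to 12% at δ = 0.5 (r 0.3 to 0.4). At δ = 0.5, 90 to 97% of those rejections say MOSES is slower. By the time-only route the rate stays at 5%.

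**The case against.** The strongest reply is that the SAP already contains the right analysis. Operative time is continuous, so the two-tailed t-test applies to it and estimates the total effect. The power sentence mentions no covariates, and the regression comes after the t-test. Reading the t-test as main and the regression as supporting is natural. This limits the harm, but the SAP does not say so, and only the regression is explicitly tied to the MOSES effect on operative time.

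Second, both links are assumed. The protocol only hypothesizes better hemostasis, and nothing gives the size or sign of the association between hematocrit and time. This stands: understatement is one branch, and overstatement is possible. At δ = 0.2 the SAP model still has at least the power of the t-test.

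Third, the excess rejections in step 6 are not plainly false in every structure. If bleeding prolongs surgery and MOSES reduces bleeding, a zero total effect requires an offsetting direct slowing, which the regression then detects. They are false under a shared cause. This also stands, so those rates carry less weight than the shift in the estimate.

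Fourth, tissue enucleated is also known only after surgery, but no passage expects the laser to change it. It needs a caveat or a substitute, not simple removal.

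**Conclusion.** The concern holds. The regression conditions on a post-randomization measure of bleeding, a declared outcome of the trial, while being described as giving the MOSES effect on operative time.

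The size is unknown. It is nil if either link is absent and at most 0.05 SD at r = 0.1 with δ up to 0.5. It is 6 to 7% of the effect at δ = 0.2, r = 0.3, and up to 24% in the grid of step 3. Stronger assumed links, as in step 5, leave 39% of the effect. Understatement requires that MOSES reduces the hematocrit fall and that a larger fall goes with longer surgery.

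This should be fixed but is not fatal, because the t-test is sound provided it is named as the main comparison. Confidence is medium, since every quantity that sets the size is assumed.

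**What to change.** 1. Remove change in hematocrit from the operative-time regression and report it as an outcome by arm.
2. State that the two-tailed t-test is the main comparison of operative time and the regression is supporting.
3. Replace tissue enucleated with prostate size if size was measured before surgery; protocol section 6.0 lists it without method or timing. Otherwise keep tissue in the supporting model, state that it is known only after surgery, and show its distribution by arm.
4. The SAP is in the past tense ("All analyses were conducted in Stata 14.2"), so results may be known. If they are, report the regression as the SAP now specifies it alongside, and disclose both the covariate change and the naming of the t-test as post hoc.

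The cost is one or two SAP sentences and one rerun, plus the disclosure in item 4 if it applies. If the laser does not affect hematocrit, removal costs 0 to 5 points of regression power (largest at r = 0.4, R² = 0.2: 89% to 84%), and nothing at r of 0.1 or less.

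Replacing tissue with preoperative size costs no power under the assumed 0.9 correlation: 84% to 86% at R² = 0.2, and 91% to 94% at R² = 0.4. Dropping tissue with no substitute would lower power from those 84% and 91% to about 79%, which is why it is kept in that case. Keeping it has its own risk. If the laser made tissue differ by an assumed 0.1 / 0.3 SD, the estimate would shift, in either direction, by 0.9 × √R² times that difference: 0.04 / 0.12 SD at R² = 0.2 and 0.06 / 0.17 SD at R² = 0.4.
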